## 6.6.1. Source data verification

Source data are: the eCRFs, Informed Consent Forms and urine bacterial analysis.

All data collected can be directly entered in the eCRF. In case site write source data in medical records or nurse notes this will be described in the site specific "Source data specification form" (sponsor ref. number VV-0201338).

Only the investigator, delegated site personnel and the sponsor representatives (personnel within Medical Affairs/Clinical Operations) will have access to all the eCRFs.

## 6.6.2. Other methods for data quality assurance

The sponsor, sponsor's representative and/or investigational sites may be inspected by competent authorities or their representatives and likewise may be audited per Coloplast internal quality audit plan and procedures.

#### 7. Statistical considerations

## 7.1. Statistical design, method and analytical procedures

Intention to Treat (ITT), Safety and Per Protocol (PP) populations will be defined at a formal data review meeting just before database lock. As a minimum, the clinical manager and the statistician will be involved in the classification of subjects.

The **ITT population** will be constituted by all randomized subjects with valid informed consent who have been exposed to at least one product, and with valid information on at least one product with respect to either primary or secondary endpoints. Any exclusion of subjects from the ITT set beyond this must be separately documented.

The **Safety population** (basis for AE summary) will be constituted by subjects that have given informed consent and have been exposed to at least one product.

The PP population will be constituted by a subset of ITT subjects

- who fulfil the inclusion/exclusion criteria
- where the primary endpoint may be evaluated for at least one of the two test days
- who do not violate the protocol in a serious way affecting the primary endpoint on all visits

Any exclusion of patients from the PP population must be documented.

Individual endpoints/data points may be excluded from analysis, even though the corresponding subject belongs to the ITT/PP population. This could for example be due to protocol violations at one test day that would affect the primary endpoint at the corresponding test day, but have no impact on the primary endpoint on the remaining test days. Any exclusion of endpoints/data points will be documented.

## Analysis of the primary endpoint

The primary endpoint is overall discomfort during catheterisation measured by VAS.

The purpose of the primary statistical analysis is to compare the discomfort level for the investigational device with that of SpeediCath® Standard Male, and measure the estimated difference against the non-inferiority margin equal to 1.2 cm. This non-inferiority margin defines the maximum value that the investigational device must fall below to be non-inferior to SpeediCath®Standard Male.

Based on data from DK058CC, DK063CC, CP235 and CP269, the average VAS discomfort level in healthy subjects is estimated to be 2.3cm. A 50% increase in the VAS mean level corresponds to an absolute difference of 1.2 cm. Hence it should be demonstrated that the mean difference between the investigational device and SpeediCath® Standard Male is less than 1.2 cm (see also section 7.2).

Let  $\mu$  investigational device be the mean discomfort level for the investigational device, and let  $\mu_{\text{SpeediCath}\otimes}$  be the corresponding mean level for SpeediCath®.

Let the null hypothesis and the alternative hypothesis be defined as:

- H0: μTestproduct μSpeediCath® > 1.2 cm
- H1: μTestproduct μSpeediCath® <1.2 cm

Non-inferiority will be demonstrated if H0 is rejected.

A mixed model with subject included as a random component will be applied for the analysis. Treatment (investigational device and SpeediCath®Standard Male) and test day (1, 2) will be included as fixed effects and age will be included as a covariate. The contrast between the investigational device and the SpeediCath® Standard Male, as well as the 95% confidence intervals will be estimated.

If the upper limit of the 95% confidence interval for the difference between the investigational device and SpeediCath® Standard Male is below 1.2,  $H_0$  is rejected and the success criterion is fulfilled.

The primary analysis will be based upon the ITT analysis set and the PP analysis set. Non-inferiority is met if this conclusion is made based on both analysis sets.

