#### Pass/fail criteria

The average discomfort score of the investigational device during catheterisation must not exceed the average discomfort score of the SpeediCath® with more than 1.2 cm on the VAS (10cm).

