### 5.2. Hypotheses

The average discomfort score of the investigational device with the new swelling media during catheterisation must not exceed the average discomfort score of the SpeediCath®Standard Male with more than 1.2 cm on the VAS (10 cm). This hypothesis will be examined statistically.

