## Analysis of the secondary endpoints

The secondary endpoints "discomfort during insertion", "discomfort during withdrawal" and "discomfort during urination post catheterisation" measured by VAS-scales will be analysed using a similar model as applied for the primary analysis. The contrast between investigational device and SpeediCath® Standard Male, as well as the 95% confidence intervals will be estimated, and a test of the hypotheses no difference between the investigational device and SpeediCath® Standard Male will be performed.

The endpoints "handling during insertion" and "handling during withdrawal" are assessed using ordinal 5 point scales. A proportional odds model with subject included as a random effect, and with treatment (investigational device and SpeediCath®Standard Male) and test day (1, 2) will be included as fixed effects and age will be included as a covariate. The odds ratio between the investigational device and SpeediCath®Standard Male as well as the corresponding 95% confidence intervals will be estimated, and a test of the hypothesis of no difference between treatments (corresponding to an odds ratio equal to 1) will be performed.

The dichotomous endpoints "need to touch the coated part of the catheter during insertion (Y/N)" and "visual blood during Catheterisation (Y/N)" will be analysed by a logistic regression model with treatment and test day as fixed effects, age is a covariate and subject is a random effect.

The negative/positive haematuria results from the urinary analysis will be analysed using a similar model as applied for the dichotomous endpoints "need to touch the coated part of the catheter during insertion (Y/N)" whereas the specific categories within positive/negative are summarised

The analysis of these endpoints will be based on the ITT population.

Adverse events will be summarized based on the safety population. Further details will be described in the statistical analysis plan.

All statistical analyses will be made with SAS version 9.4 (SAS Institute Inc., Cary, NC).

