#### 7.2. Sample size

This is a non-inferiority investigation, with a non-inferiority limit of 1.2 cm.

Based on data from trials DK058CC (SST journal number 8313-39 and Ethics Committee journal number H-D-2008-122) and CP063CC (SST journal number 8313-60 and Ethics Committee journal number H-2-2009-127), CP235 (SST journal number 2012122585 and Ethics Committee journal number H-3-2012-173) and CP269(SST journal number 2016071463 and Ethics Committee journal Number H-16033335) the standard deviation of VAS discomfort associated with SC is assumed to be 1.6, and the within subject correlation to be 0.5. The average VAS discomfort level in healthy subjects using SpeediCath®Standard Male was estimated to be 2.3 cm. Based on Li et al¹ it is assumed that a 50% increase is considered clinical relevant. Therefore, the non-inferiority limit of 1.2 cm is considered reasonable.

The effective number of subjects needed to obtain 85% power to demonstrate that a investigational device is non-inferior to SpeediCath®Standard Male is 18. The power has been calculated under the assumptions of standard deviation and within subject correlation mentioned above, and that the distribution of VAS is assumed to be the same for the investigational device as for SpeediCath®Standard Male.

The primary analysis is performed on the ITT analysis set as well as the PP analysis set. With a drop-out rate at 20%, 22 subjects will be included.

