#### 7.5. Pass/fail criteria

The success criteria for a investigational device, is that non-inferiority to SpeediCath®Standard Male in relation to the primary endpoint discomfort (max difference in VAS of +1.2 cm) is demonstrated.

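### Is the 1.2 cm non-inferiority margin wrong because 50% of 2.3 cm is 1.15 cm?

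*Combined protocol and SAP*

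**What the plan says.** Section 7.1 (Analysis of the primary endpoint) estimates the mean VAS discomfort of healthy subjects from four earlier studies at 2.3 cm and then states: "A 50% increase in the VAS mean level corresponds to an absolute difference of 1.2 cm". Non-inferiority is shown if the upper limit of the 95% confidence interval for the difference, investigational device minus comparator, is below 1.2, in both the ITT and the PP analysis sets.

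Section 7.2 repeats the basis: "The average VAS discomfort level in healthy subjects using SpeediCath®Standard Male was estimated to be 2.3 cm". Citing a published study, it adds that "it is assumed that a 50% increase is considered clinical relevant", and concludes: "Therefore, the non-inferiority limit of 1.2 cm is considered reasonable". It assumes a standard deviation of 1.6, a within-subject correlation of 0.5 and the same VAS distribution for both catheters. From these it obtains 18 effective subjects for 85% power, and it enrols 22 to allow for 20% drop-out.

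The same 1.2 cm appears in the synopsis (Pass/fail criteria), section 5.2 and section 7.5. Nowhere do the documents say that the figure was rounded.

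**The concern.** The 50% increase is the only justification offered for the margin, and the plan itself treats an increase of that size as clinically relevant. A non-inferiority margin should not be larger than the difference it is meant to exclude. Half of 2.3 cm is 1.15 cm, so the margin lies slightly above that difference, and section 7.1 presents the two as matching.

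If the upper confidence limit fell between 1.15 and 1.20 cm, the trial would succeed without having excluded a 50% increase. The rounding also enters the sample size, because 18 subjects reach the 85% target at 1.2 cm but not at 1.15 cm. Since this threshold alone decides success, even a small discrepancy has to be measured before it is set aside.

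**Working it through.** **Inputs.** Mean 2.3 cm and a 50% increase (sections 7.1 and 7.2); SD 1.6, correlation 0.5, true difference 0, 18 evaluable and 22 enrolled subjects (section 7.2). The 95% interval is taken as two-sided, so the test is one-sided at 2.5%. The plan does not state this, but a one-sided 5% test would need only 15 subjects, which does not match the stated 18.

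**The margin.**
- 0.5 × 2.3 = 1.15 cm; 1.2 / 2.3 = 52.2%.
- Excess: 1.20 − 1.15 = 0.05 cm.
- Exactly 1.200 cm would need a mean of 1.2 / 0.5 = 2.40 cm. At one decimal, however, means from 2.30 to just under 2.35 give 1.15 to 1.175 cm, which is written as 1.2.
- Means from 2.25 to just under 2.30 give 1.125 to just under 1.15 cm, which would be written as 1.1. The unrounded mean is not in the documents.

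**The plan's own sample size.**
- SD of the within-subject difference: √(2 × 1.6² × (1 − 0.5)) = 1.6 cm.
- Standard error with 18 subjects: 1.6 / √18 = 0.377 cm.
- Power comes from the non-central t distribution with n − 1 degrees of freedom and non-centrality margin / SE. With 18 subjects and a 1.2 cm margin it is 85.0%; with 17 it is 82.7%. The stated 18 subjects for 85% power is reproduced.

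**What a 1.15 cm margin would change.**

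| Evaluable subjects | Power, margin 1.2 cm | Power, margin 1.15 cm |
|---|---|---|
| 18 | 85.0% | 81.9% |
| 20 | 88.9% | 86.2% |
| 22 | 91.8% | 89.5% |

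With 19 subjects, power at 1.15 cm is 84.2%, so the 85% target would need 20 evaluable subjects. At 20% drop-out that means 20 / 0.8 = 25 enrolled, or 20 × 1.2 = 24 if inflated as the plan appears to do (18 × 1.2 = 21.6, giving 22).

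**Effect on the verdict, 18 subjects.**
- 0.05 / 0.377 = 0.13 standard errors.
- True difference 1.20 cm: chance of passing 2.5%, as intended.
- True difference 1.15 cm: chance of passing 3.3% (3.4% with 22 subjects) instead of 2.5%.
- Upper limit between 1.15 and 1.20 cm: 85.0 − 81.9 = 3.1% of trials if the true difference is 0, and 41.7 − 36.9 = 4.8% if it is 0.5 cm.

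**How firm is the benchmark?** The 2.3 cm is an estimate. With SD 1.6 and independent subjects (an assumption), the standard error of half the mean is 0.5 × 1.6 / √n = 0.8 / √n. The documents do not give the number of earlier subjects, so a range is needed: n = 64 gives 0.10 cm, n = 100 gives 0.08 cm, n = 256 gives 0.05 cm. Unless the earlier studies contributed more than 256 subjects, the discrepancy is no larger than one standard error of the benchmark.

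**The case for a change.** The strongest opposing argument is that a margin is a limit, not a descriptive statistic. Rounding a limit upward admits results that its own rationale would exclude, and a reader of section 7.1 is not told that rounding took place. Because the 50% increase is the sole rationale, and 18 subjects meet the power target only at the rounded value, a note before results are known would cost almost nothing.

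The arithmetic in this argument stands, and so does the observation that the rounding is not declared. The consequence does not:

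- The text says that 50% corresponds to 1.2 cm and that the limit is reasonable. That is a judgement made at one-decimal precision, on a benchmark the plan itself calls an assumption. It cannot separate 50% from 52%.
- The 3.1% of trials affected at a true difference of 0 are correct passes for an equivalent device, not errors.
- The plan requires success in both ITT and PP, so the joint chance of passing cannot exceed the single-test figures above.
- A stated comparison with 1.15 cm would add nothing, since the 95% interval is estimated in any case and can be read against any value.

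Moving the margin to 1.15 cm would alter the primary hypothesis and pass rule through the amendment procedure in section 9. It would also either accept power below the plan's target or require more subjects, all for half a millimetre.

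**Conclusion.** The concern does not call for a change. Half of 2.3 cm is 1.15 cm, and the plan writes this as 1.2 cm without saying that it rounded. This is a clerical looseness in one sentence of the rationale, not a wrong threshold. The documents give no sign that the value was chosen to make success easier.

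The margin is prespecified and consistent throughout, it reproduces the stated power and sample size, and the test holds its error rate against the null the plan states. The cost of the rounding is 0.05 cm, or 3.3% instead of 2.5% at a true difference of exactly 1.15 cm. The alternative costs 3.1 points of power with 18 subjects. A phrase acknowledging the rounding would be harmless but would alter no analysis, sample size or conclusion.

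This rests on the plan's SD of 1.6 and correlation of 0.5, on a two-sided 95% interval, and on a paired t calculation as an approximation to the planned mixed model. With n − 2 degrees of freedom instead, power at 1.2 cm with 18 subjects is 84.8%, which leaves the conclusion unchanged. Whether a 50% increase is the right benchmark is a separate question that this check does not settle.

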## Analysis of the secondary endpoints

The secondary endpoints "discomfort during insertion", "discomfort during withdrawal" and "discomfort during urination post catheterisation" measured by VAS-scales will be analysed using a similar model as applied for the primary analysis. The contrast between investigational device and SpeediCath® Standard Male, as well as the 95% confidence intervals will be estimated, and a test of the hypotheses no difference between the investigational device and SpeediCath® Standard Male will be performed.

The endpoints "handling during insertion" and "handling during withdrawal" are assessed using ordinal 5 point scales. A proportional odds model with subject included as a random effect, and with treatment (investigational device and SpeediCath®Standard Male) and test day (1, 2) will be included as fixed effects and age will be included as a covariate. The odds ratio between the investigational device and SpeediCath®Standard Male as well as the corresponding 95% confidence intervals will be estimated, and a test of the hypothesis of no difference between treatments (corresponding to an odds ratio equal to 1) will be performed.

The dichotomous endpoints "need to touch the coated part of the catheter during insertion (Y/N)" and "visual blood during Catheterisation (Y/N)" will be analysed by a logistic regression model with treatment and test day as fixed effects, age is a covariate and subject is a random effect.

The negative/positive haematuria results from the urinary analysis will be analysed using a similar model as applied for the dichotomous endpoints "need to touch the coated part of the catheter during insertion (Y/N)" whereas the specific categories within positive/negative are summarised

The analysis of these endpoints will be based on the ITT population.

Adverse events will be summarized based on the safety population. Further details will be described in the statistical analysis plan.

All statistical analyses will be made with SAS version 9.4 (SAS Institute Inc., Cary, NC).

#### 7.2. Sample size

This is a non-inferiority investigation, with a non-inferiority limit of 1.2 cm.

Based on data from trials DK058CC (SST journal number 8313-39 and Ethics Committee journal number H-D-2008-122) and CP063CC (SST journal number 8313-60 and Ethics Committee journal number H-2-2009-127), CP235 (SST journal number 2012122585 and Ethics Committee journal number H-3-2012-173) and CP269(SST journal number 2016071463 and Ethics Committee journal Number H-16033335) the standard deviation of VAS discomfort associated with SC is assumed to be 1.6, and the within subject correlation to be 0.5. The average VAS discomfort level in healthy subjects using SpeediCath®Standard Male was estimated to be 2.3 cm. Based on Li et al¹ it is assumed that a 50% increase is considered clinical relevant. Therefore, the non-inferiority limit of 1.2 cm is considered reasonable.

The effective number of subjects needed to obtain 85% power to demonstrate that a investigational device is non-inferior to SpeediCath®Standard Male is 18. The power has been calculated under the assumptions of standard deviation and within subject correlation mentioned above, and that the distribution of VAS is assumed to be the same for the investigational device as for SpeediCath®Standard Male.

The primary analysis is performed on the ITT analysis set as well as the PP analysis set. With a drop-out rate at 20%, 22 subjects will be included.

## 7.3. Level of significance and power

For information regarding the power and the significance level, see section 7.2.

#### 7.4. Drop-out

Based on previous investigations on similar subject population the drop-out rate is expected to be 20%.

#### 7.5. Pass/fail criteria

The success criteria for a investigational device, is that non-inferiority to SpeediCath®Standard Male in relation to the primary endpoint discomfort (max difference in VAS of +1.2 cm) is demonstrated.

### 7.6. Interim analysis

There is no planned interim analysis in this investigation.

## 7.7. Statistical reason for termination of investigation

There will be no interim analysis and therefore no reason to terminate the investigation based on statistical considerations.

## 7.8. Deviation(s) from the statistical plan

Any deviations from the statistical plan will be documented in the clinical investigation report.

### 8. Data management

## 8.1. Data review, database cleaning, and issuing and resolving data queries

Data management and statistical analysis is carried out by Medical Affairs, Coloplast A/S.

Data Management is responsible for control of data consistency and for completeness of data from each subject.

Discrepancies are listed on the Data Query Forms (DQF) and the investigator is responsible for resolving these promptly. When all DQFs are resolved, the database is locked and the statistical analyses are performed.

## 8.2. Verification, validation and securing of electronic clinical data systems

Rave EDC, version 2018.2.2, system delivered by Medidata Solutions Inc., is used for data management. The system is designed to be compliant with the FDA requirements of 21 CFR part 11. It is a validated data management system allowing only qualified and trained personnel to enter the system.

#### 8.3. Data retention

The sponsor file must be archived for a minimum period of 10 years after the final clinical investigation report has been signed.

All investigation site documents must be archived for a minimum period of 10 years after the final clinical investigation report has been signed. The Clinical manager or delegate is responsible for informing the investigator if this period should be longer for their sites per local regulation.

## 9. Amendments to the Clinical Investigation Plan

Any significant changes to the CIP must be:

- Agreed between the sponsor and the Principal investigator
- Justified in a statement included in the amended section. The version number and date of amendment must be documented

- Registered in the Change Log
- Notified to or approved by the Ethical Committee of the Capital Region of Denmark and by the Danish Medicine Agency before implementation

Examples of significant changes include: changes to inclusion criteria, endpoints or assessment methods.

## 10. Clinical Investigation Plan deviations / violations

#### 10.1. Deviations

Deviations to Clinical Investigation Plan occurs when the activities during the clinical investigation diverge from the EC approved investigation plan.

A deviation does not increase risk or decrease benefit or; does not have a significant effect on the subject's rights, safety or welfare; and/or on the integrity of the data.

#### Examples of deviations:

- Vital signs obtained prior to informed consent
- Urine dipstick is completed, but not sent for formal urine analysis
- Partly completing required tests

The Investigator is not allowed to deviate from the CIP unless under emergency circumstances and to protect the rights, safety and well-being of the subject(s).

Deviations must be reported to sponsor and deviations affecting the scientific aspect of the investigation or the safety of the subject are reported to the EC by sponsor.

#### 10.2. Violations

Violations to the Clinical Investigation Plan occurs when there is divergence from the EC approved investigation plan (a deviation) that also:

- Reduces the quality or completeness of the data
- · Impacts a subject's safety, rights or wellbeing
- Affects the scientific integrity

#### Examples of violations:

- Inadequate informed consent
- Enrolment of subjects not meeting the inclusion / exclusion criteria
- Initiation of study procedure prior to completion of informed consent
- Unreported SAE's
- Repeated deviations of the same nature
- Falsification

If any deviations and/or violations to the investigation plan are detected, the Clinical Manager or delegate will complete a Deviation/Violation Form and inform/discuss with the Principal Investigator immediately.

In case of continued or repeated violations affecting the scientific aspect of the investigation or the subjects' rights, safety and well-being sponsor will disqualify the PI from further participation in the investigation.

The Clinical Manager or delegate must report all violations detected during a monitoring visit in the Periodic Monitoring Report.

